#### 12.1.3.4 Exploratory endpoints

Exploratory endpoints include the following:

- Future biological research, (see Appendix H)
- Future genetic research, (see Appendix F)
- Change from baseline in HbA1c, FPG, HOMA- $\beta$  and achievement of HbA1c  $\leq 6.5\%$  and <7% (every year and end of the study visit)

#### 12.1.3.5 Safety endpoints

Safety is evaluated by the following endpoints:

• Secondary safety endpoints:

- Incidence of overall AEs and AEs of special interest
- Other safety endpoints:
  - Changes from baseline in laboratory tests, pulse, BP, waist circumference and body weight
  - Incidence of hypoglycaemic events, cancers and peripheral oedemas

## **12.2** Methods of statistical analyses

### 12.2.1 Demographics and baseline characteristics

Demographic and baseline characteristics will be summarised, using frequency distributions and summary statistics based on the ITT data set, for each treatment group as well as for all patients combined. Key baseline characteristics will be summarised. No statistical test will be performed for comparison of any baseline measurement among treatment groups.

Demographic and baseline characteristics will be summarised for the total study population. An additional summary of demographic and baseline characteristics will be done for patients with moderate and severe renal function (patients with baseline estimated GFR <50 mL/min).

### 12.2.2 Safety analyses

The primary safety endpoint is the time to first event included in the composite endpoint of CV death, non-fatal MI or non-fatal ischaemic stroke. The primary safety analysis will be based on the ITT population, using events adjudicated and confirmed by the independent CEC.

The baseline value of each laboratory parameter or physical examination endpoint is defined as the last assessment before the date and when available, time of the first dose of double-blind study drug.

The number and percent of patients with an AE will be summarised for each treatment group. Changes from baseline to each scheduled time point for each clinical laboratory test, BP and pulse will be summarised by treatment group. In addition, the number and percent of patients with a predefined marked abnormality in clinical laboratory tests will be summarised by treatment group.

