#### Visit 1 (0 month)

All potentially eligible patients will undergo a combined screening/enrolment/randomisation visit (may be performed during a period of 14 days) following their signed informed consent. If the patient has been clinically stable, HbA1c and serum creatinine values performed within the prior 6 months may be used to determine eligibility and treatment dose. If they have not been measured within 6 months, they should be performed as part of the screening assessments before randomisation to determine eligibility.

Following an 8-hour fast, the patients will have screening evaluations performed. Demography, medical history, and concomitant medication will be recorded. Women of childbearing potential will be tested for pregnancy. A physical examination and vital signs (pulse and BP), height and weight, waist circumference, as well as blood sampling for laboratory assessments of HbA1c, FPG, insulin, complete blood count (CBC) with differential, serum creatinine, total bilirubin (TB), alanine aminotransferase (ALT) and aspartate aminotransferase (AST), and limited urinalysis (for assessment of albumin and creatinine) will be done. Standard 12-lead electrocardiogram (ECG) readings will be recorded. Optional addenda to the informed consent for biological research and genetic research, respectively, will be obtained. The PRO questionnaire (EQ-5D) is to be completed. See Section 6.2 for further details on data collection. Patients who cannot complete the procedures required in the screening/enrolment/randomisation visit may split the visit and complete it within 14 days. Patients meeting all inclusion criteria and with no exclusion criteria will be randomised in a 1:1 ratio to receive either saxagliptin or placebo. Diet and life-style advice will be given.

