-  EQ-5D: In addition to annual assessment, the EQ-5D will be completed at the visit after any event included in the composite endpoint of CV death, non-fatal MI, or non-fatal ischaemic stroke has occurred.
-  Blood samples to be drawn at Visits 1 and 5 or at the End of Treatment visit in case of premature discontinuation of IP or if patient has not had a Visit 5 sample drawn at time of study closure, following the specific informed consent; refer to Appendix H (Biological Research).
-  Blood sample may be drawn after Visit 1 following the specific informed consent; refer to Appendix F (Pharmacogenetic Research).
-  To be recorded also for patients who prematurely discontinued IP, includes all AEs and all events comprised by the primary objectives (efficacy and safety) and the secondary efficacy objective.

 Total-Cholesterol, LDL-Cholesterol, HDL-Cholesterol, and TG.

A description of the visit structure including the window for completion of the planned visits is depicted in Table 4.

Visit ID	Visit description	Visit window
Visit 1	Enrolment/Randomisation	Can be performed over 14 days. Visit 1 date is the day the patient is randomised and receives IP, Day 0
Visit 2	Treatment	6 months (±14 days) after Visit 1
Visit 3	Treatment	12 months (±14 days) after Visit 1
Visit 4	Treatment	18 months (±14 days) after Visit 1
Visit 5	Treatment	24 months (±14 days) after Visit 1
Visit 6	Treatment	30 months (±14 days) after Visit 1
Visit 7	Treatment	36 months (±14 days) after Visit 1
Visit 8	Treatment	42 months (±14 days) after Visit 1
Visit 9	Treatment	48 months (±14 days) after Visit 1
Visit 10	Treatment	54 months (±14 days) after Visit 1
Visit $X^1$	Treatment	XX months (±14 days) after Visit 1
	End of Treatment  /Closing Visit	60 months (±14 days) after Visit 1 or within 4 weeks of the study closing date

Table 4Visit design and visit windows

Repeated visits as needed.

 EoT assessments will be done at a planned or unscheduled visit when a patient is prematurely discontinuing randomised treatment.

Telephone contacts every third month will also have a  $\pm 14$  days visit window

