# 11. EVALUATION AND CALCULATION OF VARIABLES BY ASTRAZENECA

## **11.1** Calculation or derivation of efficacy variable(s)

The primary efficacy endpoint is the time to the first event included in the composite endpoint of CV death, non-fatal MI or non-fatal ischaemic stroke. For this endpoint and for the secondary time-to-event endpoints, the time from randomisation to event or time to last documented contact for patients with no event will be calculated.

A patient may have 1 or more events. However, only a patient's first occurring event will contribute to the analysis of the specified variable.

Only events adjudicated and confirmed by the CEC will be included in the primary and secondary time to CV event analyses.

Total days of hospitalisation will be calculated as the date of discharge from the hospital minus the date admitted to hospital + 1. For each patient, the baseline for glycaemic measures (eg, HbA1c) are defined as the last assessment before the first dose of double-blind study drug. Change from baseline to any randomised treatment period Month t is defined as follows:

*CMonth t* = *MMonth t* - *Mbaseline*, where:

- CMonth t is the change from baseline at Month t
- MMonth t is the measurement at Month t
- Mbaseline is the baseline measurement

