# **11.2** Calculation or derivation of safety variable(s)

The baseline value of each safety laboratory test or physical exam endpoint is defined as the last assessment before the date and (where available) time of the first dose of double-blind study drug.

Change from baseline will be calculated using the same method as for glycaemic efficacy variables.

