### 12.1.2 Safety analysis set

The safety population will be identical to the ITT population.

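### Read literally, the safety baseline rule excludes Visit 1 values taken on the date of first dose whenever no dose time is recorded

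*Protocol*

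**What the plan says.** The protocol gives two kinds of baseline rule.

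- **Safety.** Section 12.2.2 uses "the last assessment before the date and when available, time of the first dose" of double-blind drug for laboratory parameters and physical examination endpoints. Section 11.2 has nearly the same wording: "the last assessment before the date and (where available) time of the first dose". Section 6.2 lists blood pressure, pulse, weight and waist circumference under the physical examination, and no separate baseline rule is given for them.
- **Glycaemic measures.** Section 11.1 says "the baseline for glycaemic measures (eg, HbA1c) are defined as the last assessment before the first dose of double-blind study drug". It makes no reference to the calendar date.

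On timing, Section 3.1 describes Visit 1 as a "combined screening/enrolment/randomisation visit (may be performed during a period of 14 days"). Table 4 fixes its date: "Visit 1 date is the day the patient is randomised and receives IP, Day 0". In Table 3 every later visit lies in the double-blind treatment period, so Visit 1 is the only scheduled source of pre-dose values.

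**The concern.** The safety rule tests against the date of first dose and refines this by time only when a time exists. The design allows the baseline assessments and the first tablet to fall on one date. If the dose time is missing, a sample drawn that morning is not before that date, and there is no other scheduled pre-dose visit to fall back on.

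At stake are the changes from baseline listed as safety endpoints in Section 12.1.3.5: laboratory tests, pulse, blood pressure, waist circumference and body weight. The rule covers every laboratory parameter, so it also reaches baseline serum creatinine, against which a doubling of creatinine (Section 12.1.3.3 and Appendix I, Section 10) would be judged.

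The two rules also disagree with each other. From one Visit 1 blood draw, HbA1c could qualify as baseline while ALT, blood count and creatinine did not.

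**Working it through.** The protocol gives no figure to reproduce. The check is to apply each rule to the situations that the schedule permits. I read the time clause in its natural sense: compare date and time when both are known, and otherwise compare the date alone.

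1. **Assessment on an earlier day of a split Visit 1.** It precedes the first-dose date. Both rules keep it.
2. **First tablet taken on a date after the assessment.** Both rules keep the value.
3. **Same date, dose and assessment times known, assessment first.** The time clause applies. Both rules keep the value.
4. **Same date, no dose time.** Sections 11.2 and 12.2.2 reduce to the date test, which a same-day value fails. Section 11.1 asks only whether the assessment preceded the dose. Section 3.1 places the screening evaluations ahead of randomisation, so a Visit 1 value passes that test by design.

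The rules part company only in case 4. Whether case 4 arises depends on what is recorded:

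- The data lists in Sections 6.2 and 6.2.1 do not include a first-dose time.
- Section 5.7 asks for administration of study drug to be recorded in the CRF, without saying whether this includes a clock time.
- Section 6.4.5 records the date and time of laboratory sampling. That is one half of the comparison.
- Section 6.4.8 mentions no time for blood pressure, pulse, weight or waist measurements, so for these a recorded dose time might still not settle the order. Section 6.4.8.1 does place pulse and blood pressure ahead of any blood sampling.

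For size, let *s* be the share of patients assessed and first dosed on the same date, and *m* the share of those with no usable dose time. The affected share is *s* × *m*. The protocol gives neither.

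- If *s* = 0 or *m* = 0, the share is 0%.
- If both approach 1, the share approaches 100%.

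The document does not narrow this range, so no patient count can be attached to the point.

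**The case against.** The strongest reply is that the loss is hypothetical. It needs a first dose on the assessment date, a missing dose time and an analyst who applies the date test strictly. The protocol establishes none of these. The time clause is there to keep same-day pre-dose values. Table 4 says that the patient receives the drug on Day 0, not that the first tablet is taken then. Visit 1 may be split over 14 days. Patients whose HbA1c or creatinine must be measured to settle eligibility need a result before randomisation, and Section 6.4.5 allows up to 72 hours for central results, so many of them would be sampled on an earlier date. All of this stands, and it makes the point conditional.

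A second reply is that same-day and missing-time conventions belong in the SAP, which was not available. That carries less weight here. The protocol does not leave the rule open. It states it twice, so a SAP that admitted same-day values would depart from the protocol's own wording.

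A reader might infer that patients who start on Day 0 have no safety baseline. The document does not support this as fact: it nowhere says that same-day values are dropped, and the three conditions above must hold together. A reader might also add the never-dosed patients, since "The safety population will be identical to the ITT population" and a patient who takes no tablet has no first dose. That gap is real but minor. Patients off treatment are followed for adverse events and clinical events only, apart from a possible end-of-treatment assessment, so they would contribute almost no change-from-baseline data.

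**Conclusion.** The point holds as a defect in a stated rule. Taken literally, Sections 11.2 and 12.2.2 exclude valid pre-dose Visit 1 values for patients first dosed on the assessment date without a recorded dose time, and they are inconsistent with Section 11.1 for measures from the same sample. The extent is unknown, from 0% to nearly all patients, and rests on two facts that the protocol does not give: how often assessment and first dose share a date, and whether a dose time is captured.

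The reach is limited. Section 12.2.2 uses the safety baseline for descriptive change summaries, and the renal measures that need a baseline creatinine may also be touched. The primary composite is time from randomisation to a first adjudicated event and does not use it. Incidence of adverse events identified by reported terms does not need it either. It would also go too far to infer a bias between the arms: the trial is double-blind, and nothing in the document suggests that recording of dose times would differ by treatment. The wording should be corrected, but the primary conclusions do not depend on it.

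**What to change.** Replace the definitions in Sections 11.2 and 12.2.2 with one that agrees in substance with Section 11.1: baseline is the last non-missing assessment on or before the date of first dose, and Visit 1 assessments made on that date count as pre-dose unless recorded times show otherwise. Using the same sentence in Section 11.1 would leave a single definition for all measures. A clause taking the randomisation date as reference for patients never dosed is optional.

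The cost is a wording change in two sections, or three if Section 11.1 is included. It needs no new data, visits or CRF fields.

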#### 12.2.3 Efficacy analyses

The primary efficacy endpoint is the time to first event included in the composite endpoint of CV death, non-fatal MI, or non-fatal ischaemic stroke. The primary efficacy analysis will be based on the ITT population, using events adjudicated and confirmed by the CEC. Secondary time to event variables will be treated similarly.

For the primary and secondary time to event variables, HRs and CIs will be derived from a Cox proportional hazards model stratified by baseline renal impairment category and by CV risk category (established CV disease, multiple risk factors without established CV disease).

The primary and secondary analyses will not be adjusted for covariates. Exploratory proportional hazards models of the primary and selected secondary endpoints will determine whether control for baseline CV risk factors has any effect on the relative risk associated with randomised treatment. A forest plot will show HRs and CIs of treatment effects within subgroups.

The primary and secondary analyses will be repeated to assess robustness of results when patients with severe renal impairment (based on baseline estimated GFR) are excluded.

The primary and secondary analyses will also be repeated for the subgroup of patients who consented to use SMS, to assess consistency of results with the overall population.

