#### **Short Message Service contacts**

In addition to standard telephone contact, patients will be asked to participate in use of a Short Message Service (SMS) technology to enhance the communication between the study site and the individual. The main purpose of this tool is patient retention because of the better "partnering" of the patient with the study site personnel. Permission from the patient to use this tool will be obtained by the study site. All patients will receive the same type messages within the major local language of their country of residence. This tool is not intended as a data collection tool.

The patient will receive messages such as 1) a reminder of their next visit; 2) reminder as to what to bring to their next visit (such as IP); 3) and messages of encouragement such as "Congratulations, you have just completed your first visit!" or "Happy Birthday".

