# 8.4 Informed consent

The PI(s) at each centre will:

- Ensure each patient is given full and adequate oral and written information about the nature, purpose, possible risk and benefit of the study
- Ensure each patient is notified that he/she is free to discontinue from the study at any time
- Ensure that each patient is given the opportunity to ask questions and allowed time to consider the information provided
- Ensure each patient provides signed and dated informed consent before conducting any procedure specifically for the study
- Ensure the original, signed ICF(s) is/are stored in the Investigator's Study File
- Ensure that ICF for the SMS use is signed and stored, if applicable
- Ensure that ICFs for the optional pharmacogenetic and/or biological sampling portions of the study are signed and stored, if applicable
- Ensure a copy of the signed ICF(s) is/are given to the patient
- Ensure that any incentives for patients who participate in the study as well as any provisions for patients harmed as a consequence of study participation are described in the informed consent form that is approved by an Ethics Committee

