# **12.** STATISTICAL METHODS AND SAMPLE SIZE

# **12.1** Description of analysis sets

### 12.1.1 Efficacy analysis set

All patients used in the analyses of the primary and secondary objectives will belong to the ITT population. This population is defined as all randomised patients. The patients will be analysed according to the treatment group to which they were randomised (not to which treatment they actually received).

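### The SMS consistency check compares a self-selected subgroup with the full trial that contains it, so a share of any real difference equal to the SMS fraction of events does not show.

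*Protocol*

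**What the plan says.** Section 12.2.3 plans the check in one sentence: "The primary and secondary analyses will also be repeated for the subgroup of patients who consented to use SMS, to assess consistency of results". The comparator follows in the same sentence; the stated purpose is "to assess consistency of results with the overall population". Section 12.1.1 says of the ITT population: "This population is defined as all randomised patients". The consenters are therefore part of their own comparator. For SMS, the protocol names neither a comparison with non-consenters nor an interaction test. The same section plans a forest plot by subgroup but does not list the subgroups.

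Membership is by the patient's choice. Under the Short Message Service heading in section 3.1, "patients will be asked to participate in use of a Short Message Service (SMS) technology", and "Permission from the patient to use this tool will be obtained by the study site". The stated aim is retention: "The main purpose of this tool is patient retention". Section 8.4 has a separate form: "Ensure that ICF for the SMS use is signed and stored, if applicable". Section 5.2.1 stratifies randomisation by renal category and CV risk category only.

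No section gives a time for SMS consent. The Visit 1 text says "Optional addenda to the informed consent for biological research and genetic research, respectively, will be obtained" and does not mention SMS; nor do Table 3 or the enrolment data list in section 6.2. No expected uptake and no criterion for consistency are stated.

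**The concern.** A consistency check on SMS use should ask whether the treatment effect differs between patients who had the retention tool and those who did not. Setting the users against a total that includes them answers a weaker question, because the users pull the overall estimate towards their own. The larger their share of the events, the closer the two hazard ratios lie, whatever the true gap. At high uptake, a reader who looks at the two numbers could call the results consistent when users and non-users differ materially.

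At stake is the usefulness of one supportive analysis, not the primary conclusion.

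**Working it through.** **The plan's own figures.** Section 12.3 gives 1040 primary events, a 17% risk reduction (HR 0.83) and 85% power at the one-sided 2.45% level. With 1:1 allocation, power = Φ(√(D/4) × |log HR| - z₁₋α) = Φ(√260 × 0.1863 - 1.969) = Φ(1.036) = 0.850. The stated 85% reproduces, so 1040 events with variance 4/D for a log hazard ratio is a sound basis. The protocol gives no figure for the SMS analysis itself.

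**Dilution.** Let f be the share of events in SMS users. Then, approximately,

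log HR(overall) = f × log HR(SMS) + (1 - f) × log HR(non-SMS).

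Subtracting from log HR(SMS):

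log HR(SMS) - log HR(overall) = (1 - f) × [log HR(SMS) - log HR(non-SMS)].

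The visible share is 1 - f and the hidden share is f.

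**Precision of the direct contrast.** SE = √(4/(fD) + 4/((1 - f)D)), with D = 1040.

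- f = 0.5: √(4/520 + 4/520) = 0.124
- f = 0.8: √(4/832 + 4/208) = 0.155

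**Illustration.** Both f and the hazard ratios here are assumptions; the protocol supplies neither. Take HR 0.70 in users and 1.00 in non-users, a true ratio of 0.70. Then overall HR = 0.70^f and the SMS/overall ratio = 0.70^(1 - f). The last column divides the SMS-overall gap by √(4/(fD) + 4/D), that is, it treats the two estimates as if they were independent.

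| f | Hidden | Overall HR | SMS/overall ratio | SE, SMS vs non-SMS | z, SMS vs non-SMS | z, SMS vs overall as if independent |
|---|---|---|---|---|---|---|
| 0.10 | 10% | 0.965 | 0.725 | 0.207 | 1.73 | 1.56 |
| 0.25 | 25% | 0.915 | 0.765 | 0.143 | 2.49 | 1.93 |
| 0.50 | 50% | 0.837 | 0.837 | 0.124 | 2.88 | 1.66 |
| 0.75 | 75% | 0.765 | 0.915 | 0.143 | 2.49 | 0.94 |
| 0.80 | 80% | 0.752 | 0.931 | 0.155 | 2.30 | 0.77 |
| 0.90 | 90% | 0.725 | 0.965 | 0.207 | 1.73 | 0.40 |

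At f = 0.75, a true 30% relative difference appears as a ratio of 0.915. Read as two separate estimates, it gives z = 0.94, where the direct contrast gives 2.49.

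**Check of the approximation.** In simulated data (200,000 patients per setting, the same two hazard ratios, equal baseline hazard), SMS patient shares of 0.25, 0.50 and 0.75 left visible shares of 0.78, 0.54 and 0.28. The matching event shares are 0.25 × 0.85 / (0.25 × 0.85 + 0.75) = 0.22, and likewise 0.46 and 0.72, where 0.85 is the mean of 0.70 and 1.00. So 1 - f = 0.78, 0.54 and 0.28, as the formula predicts.

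**The case against.** Several counter-arguments have weight.

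- **A reader might infer that the check hides most of any real difference.** The documents do not support that. It needs f above 0.5, and no uptake is stated; at f = 0.10 only a tenth is hidden. For the same reason one cannot say that the check will report consistency whatever the non-SMS patients show. This objection stands.
- **No information is destroyed.** With both hazard ratios and the event counts, the non-SMS log hazard ratio can be recovered as (overall - f × SMS)/(1 - f). If the overlap is allowed for in the standard error, the SMS-overall contrast has the same z as the interaction. This is true, but section 12.2.3 describes no such step, and a side-by-side reading of the two hazard ratios would miss it.
- **Interaction tests are commonly left to the SAP.** They are, and their absence alone would be no finding. What remains is that the protocol itself names the comparator, and names one that contains the subgroup.
- **A reader might also infer that SMS status is set after randomisation, so that patients who die or leave early cannot enter the subgroup.** The protocol does not say this; it is silent on timing. One of its sample messages congratulates the patient on completing the first visit, which points to permission at about Visit 1 without requiring it. Late consent is expressly allowed for the genetic sample (section 4.1), and nothing similar is said for SMS. Double-blind treatment, and the same type of message for all patients, make a difference between arms from late consent probably small. No size can be given.
- **Nothing depends on the result.** The SMS repeat is outside the test sequence, has no alpha and triggers no decision. This stands and sets the priority.

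**Conclusion.** The point holds in limited form. Section 12.2.3 judges a self-selected, non-stratified subgroup against the ITT population that contains it, and this shows only (1 - f) of the log hazard ratio difference between SMS and non-SMS patients. The dilution formula assumes that the overall estimate is roughly the event-weighted average of the two groups; the simulation supports this. The amount hidden depends wholly on f, which the protocol does not state: 10%, 50% and 80% at f = 0.10, 0.50 and 0.80 are illustrations across a range, not estimates for this trial.

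The timing of SMS consent is a secondary point, inferred from silence and probably of small effect. Importance is low: the primary and confirmatory secondary tests are unaffected.

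**What to change.** In section 12.2.3, or in the SAP, replace the comparison with the overall population by hazard ratios and confidence intervals for SMS and non-SMS patients side by side, for the primary and secondary endpoints. Add a treatment-by-SMS interaction term to the stratified Cox model and report the ratio of hazard ratios with its interval. For the primary endpoint at 1040 events, the 95% limits lie at the estimate divided and multiplied by about exp(1.96 × 0.124) = 1.28 at f = 0.5 and exp(1.96 × 0.155) = 1.36 at f = 0.8. A non-significant interaction should therefore not be read as proof of consistency. State the number of SMS patients and their events.

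Where consent dates allow, define SMS status by consent given at or before randomisation, and count later consenters as non-SMS.

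The comparison itself needs only a change of wording: the data are the same, no alpha is spent and the primary test does not change. The timing rule may not be free. Section 6.2 lists consent dates for biological and genetic research but none for SMS, and section 12.3 refers to an observed event rate, so the trial is already running. If no SMS consent dates exist, say so and report the comparison with that limitation.
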